4.5.8 Laboratory and Biomarker Samples

All of the laboratory tests will be conducted by the trial site's local laboratory. Biomarker samples will first be sent to a central laboratory and then to outsourced contract research organizations (CROs) or the Sponsor for testing.

The following laboratory and biomarker samples will be collected:

- Hematology: white blood cell (WBC) count, red blood cell (RBC) count, hemoglobin, hematocrit, platelet count, differential count (neutrophils, eosinophils, basophils, monocytes, lymphocytes, other cells)
- Chemistry panel (serum or plasma): sodium, potassium, chloride, bicarbonate, glucose, blood urea nitrogen (BUN) or urea, creatinine, total protein, albumin, phosphorus, calcium, total and direct bilirubin, alkaline phosphatase, ALT, AST, uric acid, lactate dehydrogenase (LDH)
- Pregnancy test:
- All women of childbearing potential will have a serum pregnancy test at screening. Urine pregnancy tests will be performed at specified subsequent visits. If a urine pregnancy test is positive, it must be confirmed by a serum pregnancy test.
- Blood samples for exploratory research on biomarkers (see [Appendix 1](#)).

Exploratory biomarker research may include, but will not be limited to CCL18, MMP7, CXCL13, and COMP.

For sampling procedures, storage conditions, and shipment instructions, see the laboratory manual.

Unless the patient gives specific consent for his or her leftover samples to be stored for optional exploratory research (see Section [4.5.11](#)), biological samples will be destroyed when the final Clinical Study Report has been completed, with the following exceptions:

- Whole blood, plasma, and serum samples collected for biomarker analyses will be destroyed no later than 5 years after the final Clinical Study Report has been completed.

When a patient withdraws from the trial, samples collected prior to the date of withdrawal may still be analyzed, unless the patient specifically requests that the samples be destroyed or local laws require destruction of the samples.

Data arising from sample analysis will be subject to the confidentiality standards described in Section [8.4](#).

4.5.9 Electrocardiograms

Single ECG recordings will be obtained at specified time points, as outlined in the Schedule of Assessments (see [Appendix 1](#)), and may be obtained at unscheduled time points as indicated.

All ECG recordings must be performed using a standard high-quality, high-fidelity digital electrocardiograph machine equipped with computer-based interval measurements. Lead placement should be as consistent as possible. ECG recordings must be performed after the patient has been resting in a supine position for at least 10 minutes. All ECGs, when possible, should be obtained prior to other procedures scheduled at the same time (e.g., vital sign measurements, blood draws). Circumstances that may induce changes in heart rate, including environmental distractions (e.g., television, radio, conversation) should be avoided during the pre-ECG resting period and during ECG recording.

For safety monitoring purposes, the investigator must review, sign, and date all ECG tracings. Paper copies of ECG tracings will be kept as part of the patient's permanent trial file at the site. Digital recordings will be stored at site. The following should be recorded in the appropriate eCRF: heart rate, RR interval, QRS interval, PR duration, uncorrected QT interval, and the QTcF based on the machine readings of the individual ECG tracings. Any morphologic waveform changes or other ECG abnormalities must be documented on the eCRF. If considered appropriate by the Sponsor, ECGs may be analyzed retrospectively at a central laboratory. Refer to section 5.1.1.8 for details on protocol management of increases in QT interval.

4.5.10 Patient-Reported Outcomes

Several PRO assessments will be conducted in this trial, including the UCSD-SOBQ, the Leicester Cough Questionnaire, the cough visual analog scale, and the SGRQ (see [Appendix 2](#)). The impact of potential bias on these outcomes will not be investigated.

PRO data will be collected via questionnaires to document the treatment effect and to evaluate the benefit of pirfenidone. The questionnaires, translated into the local language as required, will be completed in their entirety at specified time points during the trial (see [Appendix 1](#)). To ensure instrument validity and that data standards meet health authority requirements, questionnaires will be self-administered before the patient

receives any information on disease status and prior to the performance of non-PRO assessments, unless otherwise specified.

4.5.11 Optional Samples for Research Biosample Repository

4.5.11.1 Overview of the Research Biosample Repository

The RBR is a centrally administered group of facilities used for the long-term storage of human biologic specimens, including body fluids, solid tissues, and derivatives thereof (e.g., DNA, RNA, proteins, peptides). The collection, storage, and analysis of RBR specimens will facilitate the rational design of new pharmaceutical agents and the development of diagnostic tests, which may allow for individualized drug therapy for patients in the future.

Specimens for the RBR will be collected from patients who give specific consent to participate in this optional research. RBR specimens will be used to achieve the following objectives:

- To study the association of biomarkers with efficacy, adverse events, or disease progression
- To increase knowledge and understanding of disease biology
- To study drug response, including drug effects and the processes of drug absorption and disposition
- To develop biomarker or diagnostic assays and establish the performance characteristics of these assays.

4.5.11.2 Approval by the Institutional Review Board or Ethics Committee

Collection and submission of biological samples to the RBR is contingent upon the review and approval of the exploratory research and the RBR portion of the Informed Consent Form by each site's Institutional Review Board or Ethics Committee (IRB/EC) and, if applicable, an appropriate regulatory body. If a site has not been granted approval for RBR sampling, this section of the protocol (Section 4.5.11) will not be applicable at that site.

4.5.11.3 Sample Collection

The following samples will be collected for research purposes, including, but not limited to, research on biomarkers related to pirfenidone or unclassifiable ILD:

- Leftover plasma, serum, and whole blood RNA (*PAX* gene) samples
- RBR whole blood for DNA extraction

The above samples may be sent to one or more laboratories for DNA extraction to enable analysis of germline mutations, somatic mutations via whole genome sequencing (WGS), next-generation sequencing (NGS), or other genomic analysis methods.

Genomics is increasingly informing researcher's understanding of disease pathobiology. WGS provides a comprehensive characterization of the genome and, along with clinical data collected in this trial, may increase the opportunity for developing new therapeutic approaches. Data will be analyzed in the context of this trial but will also be explored in aggregate with data from other studies. The availability of a larger dataset will assist in identification of important pathways, guiding the development of new targeted agents.

For sampling procedures, storage conditions, and shipment instructions, see the laboratory manual.

RBR specimens are to be stored until they are no longer needed or until they are exhausted. However, the RBR storage period will be in accordance with the IRB/EC-approved Informed Consent Form and applicable laws (e.g., health authority requirements).

4.5.11.4 Confidentiality

Specimens and associated data will be labeled with a unique patient identification number.

Patient medical information associated with RBR specimens is confidential and may be disclosed to third parties only as permitted by the Informed Consent Form (or separate authorization for use and disclosure of personal health information) signed by the patient, unless permitted or required by law.

Given the complexity and exploratory nature of the analyses, data derived from RBR specimens will generally not be provided to trial investigators or patients unless required by law. The aggregate results of any conducted research will be available in accordance with the effective Sponsor policy on trial data publication.

Data generated from RBR specimens must be available for inspection upon request by representatives of national and local health authorities, and Sponsor monitors, representatives, and collaborators, as appropriate.

Any inventions and resulting patents, improvements, and/or know-how originating from the use of the RBR data will become and remain the exclusive and unburdened property of the Sponsor, except where agreed otherwise.

4.5.11.5 Consent to Participate in the Research Biosample Repository

The Informed Consent Form will contain a separate section that addresses participation in the RBR. The investigator or authorized designee will explain to each patient the objectives, methods, and potential hazards of participation in the RBR. Patients will be told that they are free to refuse to participate and may withdraw their specimens at any time and for any reason during the storage period. A separate, specific signature will be required to document a patient's agreement to provide optional RBR specimens. Patients who decline to participate will not provide a separate signature.

The investigator should document whether or not the patient has given consent to participate and (if applicable) the date(s) of consent, by completing the RBR Research Sample Informed Consent eCRF.

In the event of an RBR participant's death or loss of competence, the participant's specimens and data will continue to be used as part of the RBR research.

4.5.11.6 Withdrawal from the Research Biosample Repository

Patients who give consent to provide RBR specimens have the right to withdraw their specimens from the RBR at any time for any reason. If a patient wishes to withdraw consent to the testing of his or her specimens, the investigator must inform the Medical Monitor in writing of the patient's wishes through use of the appropriate RBR Patient Withdrawal Form and, if the trial is ongoing, must enter the date of withdrawal on the RBR Research Sample Withdrawal of Informed Consent eCRF. The patient will be provided with instructions on how to withdraw consent after the trial is closed. A patient's withdrawal from this trial does not, by itself, constitute withdrawal of specimens from the RBR. Likewise, a patient's withdrawal from the RBR does not constitute withdrawal from this trial.

4.5.11.7 Monitoring and Oversight

RBR specimens will be tracked in a manner consistent with Good Clinical Practice by a quality-controlled, auditable, and appropriately validated laboratory information management system, to ensure compliance with data confidentiality as well as adherence to authorized use of specimens as specified in this protocol and in the Informed Consent Form. Sponsor monitors and auditors will have direct access to appropriate parts of records relating to patient participation in the RBR for the purposes of verifying the data provided to the Sponsor. The site will permit monitoring, audits, IRB/EC review, and health authority inspections by providing direct access to source data and documents related to the RBR samples.

4.6 PATIENT, TREATMENT, TRIAL, AND SITE DISCONTINUATION

4.6.1 Patient Discontinuation

Patients have the right to voluntarily withdraw from the trial at any time for any reason. In addition, the investigator has the right to withdraw a patient from the trial at any time.

Reasons for withdrawal from the trial may include, but are not limited to, the following:

- Patient withdrawal of consent at any time
- Any medical condition that the investigator or Sponsor determines may jeopardize the patient's safety if he or she continues in the trial
- Investigator or Sponsor determines it is in the best interest of the patient
- Patient non-compliance, defined as non-adherence with the dosing regimen, including the dose-titration guidance for starting trial treatment
- Lung transplantation

Patients who undergo lung transplantation during the trial will be discontinued at the time of hospitalization for transplantation.

Every effort should be made to obtain information on patients who withdraw from the trial. The primary reason for withdrawal from the trial should be documented on the appropriate eCRF. However, patients will not be followed for any reason after consent has been withdrawn. Patients who withdraw from the trial will not be replaced.

4.6.2 Trial Treatment Discontinuation

Patients must discontinue trial treatment if they experience any of the following:

- Pregnancy
- Hepatic or renal impairment
- LFT elevations that require discontinuation
- Angioedema

The primary reason for early trial treatment discontinuation should be documented on the appropriate eCRF. Patients who discontinue trial treatment prematurely will not be replaced.

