4.3.4 Continued Access to Pirfenidone

After completion of the double-blind treatment period, the Sponsor will offer the possibility to the patients to receive continued access to pirfenidone in a safety follow-up period of up to 12 months, within this clinical trial protocol. A final Follow-up Visit will be performed at the end of the safety period, 28 days after the last open-label dose.

At the end of the 24-week double-blind treatment period, in order to maintain blinding, all patients will discontinue treatment over a 28-day period and return for the Follow-up Visit.

For patients who could benefit from participating in the 12-month safety follow-up period, according to the investigator's judgment, open-label pirfenidone will be started on the 28-day Follow-up Visit, using the titration schedule in [Table 2](#) . During the 12-month safety follow-up period, initially, patients will be evaluated at monthly visits for the first 6 months. At the end of the first 6 months, patients will be evaluated at each site visit occurring approximately every 3 months until the end of the safety follow-up period. In addition, at the end of the first 6 months, patients will perform home pregnancy tests at each month where there is no site visit. Patients will be provided with home pregnancy test kits and will be instructed to contact the site immediately should the test result be positive. In such cases, the patient must visit the site for a confirmatory serum pregnancy test. Refer to Schedule of Assessments for the assessments to be performed during this safety follow-up period ([Appendix 1](#)). The dose of pirfenidone used during the safety follow-up period is in accordance to section 4.3.2.1.

Following the end of the 12-month safety follow-up period, the Sponsor will offer post-trial access to the trial treatment (pirfenidone), free of charge, to eligible patients in accordance with the Roche Global Policy on Continued Access to IMP, as outlined below.

A patient will be eligible to receive Pirfenidone (Esbriet®) after completing the trial if all of the following conditions are met:

- The patient has a life-threatening or severe medical condition and requires continued trial treatment for his or her well-being
- There are no appropriate alternative treatments available to the patient
- The patient and his or her doctor comply with and satisfy any legal or regulatory requirements that apply to them.

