5. ASSESSMENT OF SAFETY

5.1 SAFETY PLAN

Pirfenidone is approved for the treatment of IPF in the US, and for the treatment of mild to moderate IPF in the EEA and Canada ([Esbriet SmPC 2015](#); [Health Canada 2016](#); [US FDA 2015](#)). However, the efficacy and safety of pirfenidone in patients with unclassifiable ILD has not been fully elucidated. The safety plan for patients in this trial is based on clinical experience with pirfenidone in completed and ongoing studies predominately involving patients with IPF. The anticipated important safety risks for pirfenidone are outlined below. Please refer to the pirfenidone Investigator's Brochure for a complete summary of safety information.

Several measures will be taken to ensure the safety of patients participating in this trial. Eligibility criteria have been designed to exclude patients at higher risk for toxicities. Patients will undergo safety monitoring during the trial, including assessment of the nature, frequency, and severity of adverse events. In addition, guidelines for managing adverse events, including criteria for dosage modification and treatment interruption or discontinuation, are provided below.

An iDMC will review safety data and advise on trial conduct (see Section [3.1](#)). The procedures that will be used by the iDMC will be detailed in an iDMC charter.

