5.3.1 Adverse Event Reporting Period

Investigators will seek information on adverse events at each patient contact. All adverse events, whether reported by the patient or noted by trial personnel, will be recorded in the patient's medical record and on the Adverse Event eCRF.

After informed consent has been obtained **but prior to initiation of trial treatment**, only serious adverse events caused by a protocol-mandated intervention (e.g., invasive procedures such as biopsies, discontinuation of medications) should be reported (see Section 5.4.2 for instructions for reporting serious adverse events).

After initiation of trial treatment, all adverse events will be reported until 28 days after the last dose of trial treatment (Follow-up Visit).

Instructions for reporting adverse events that occur after the adverse event reporting period are provided in Section 5.6.

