Appendix 1 Schedule of Assessments

	Washout ^a	Screening	Double-blind treatment							Early treatment discontinuation ^b	Follow-up ^u	Additional safety follow-up ^c	Additional safety follow-up final visit
Day Week	-50 to -22	-21 to -1	Randomization 1 1	28 4	56 8	84 12	112 16	140 20	168 24		196 28	up to 12 months	up to 12 months plus 28 days
Window (days, unless otherwise stated)				±5	±5	±5	±5	±5	±5	±5 ^b	±5	±5	±5
Treatment Period Visit			1	2	3	4	5	6	7			Month 1 to 6: Monthly visits Month 7 to 12: Approximately every 3 months	
Informed consent ^{d,e}	x	x											
Review Eligibility Criteria		x											
Demographic data ^e	x	x											
General medical history and baseline conditions ^e	x	x											
Vital signs ^f		x	x	x	x	x	x	x	x	x	x	x	
Weight		x							x	x			
Height		x											
Complete physical examination ^g		x	x						x	x			

	Washout ^a	Screening	Double-blind treatment							Early treatment discontinuation ^b	Follow-up ^u	Additional safety follow-up ^c	Additional safety follow-up final visit
Day Week	-50 to -22	-21 to -1	Randomization 1 1	28 4	56 8	84 12	112 16	140 20	168 24		196 28	up to 12 months	up to 12 months plus 28 days
Window (days, unless otherwise stated)				±5	±5	±5	±5	±5	±5	±5 ^b	±5	±5	±5
Treatment Period Visit			1	2	3	4	5	6	7			Month 1 to 6: Monthly visits Month 7 to 12: Approximately every 3 months	
ECG ^h		x	x			x			x	x	x		
Hematology ⁱ		x	x			x			x	x			
Chemistry ^j		x	x	x	x ^k	x	x ^k	x ^k	x	x		x ^k	
Pregnancy test ^l		x	x	x	x	x	x	x	x	x		x	
Trial treatment administration			x	x	x	x	x	x			x ^m	x	
Spirometry (FVC, FEV ₁)		x	x	x	x	x	x	x	x	x			
Daily spirometry (handheld device) ^{n,o}		x	x	x	x	x	x	x	x	x			
DLco		x	x			x			x	x			
6MWD ^p		x	x			x			x	x			
Leicester Cough Questionnaire ^q			x			x			x	x			
UCSD-SOBQ ^q			x			x			x	x			

	Washout ^a	Screening	Double-blind treatment							Early treatment discontinuation ^b	Follow-up ^u	Additional safety follow-up ^c	Additional safety follow-up final visit
Day Week	-50 to -22	-21 to -1	Randomization 1 1	28 4	56 8	84 12	112 16	140 20	168 24		196 28	up to 12 months	up to 12 months plus 28 days
Window (days, unless otherwise stated)				±5	±5	±5	±5	±5	±5	±5 ^b	±5	±5	±5
Treatment Period Visit			1	2	3	4	5	6	7			Month 1 to 6: Monthly visits Month 7 to 12: Approximately every 3 months	
SGRQ ^q			x			x			x	x			
Cough visual analog score ^q			x			x			x	x			
Serum for biomarker assessments			x	x		x			x	x			
Plasma for biomarker assessments			x	x		x			x	x			

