- ^c After completion of the double-blind treatment period and the Follow-up Visit at Week 28, the Sponsor will offer the possibility to the patients to receive open-label pirfenidone within the trial protocol in a safety follow-up period of up to 12 months. During the 12-month safety follow-up period, initially, patients will be evaluated at monthly visits for the first 6 months. At the end of the first 6 months, patients will be evaluated at each site visit occurring approximately every 3 months until the end of the safety follow-up period.. A final Follow-up Visit will be performed at the end of the safety period, 28 (± 5) days after the last open-label dose.
- ^d Informed consent must be documented before any trial-specific screening procedure is performed, and may be obtained either at the Washout or Screening Visits.
- ^e Any procedures that were not completed during washout, must be completed at the Screening Visit.
- ^f Includes respiratory rate, pulse rate, and systolic and diastolic blood pressures while the patient is in a seated position, and temperature. Abnormalities observed at baseline should be recorded on the General Medical History and Baseline Conditions eCRF. At subsequent visits, new or worsened clinically significant abnormalities should be recorded on the Adverse Event eCRF. All vital sign measurements are to be obtained prior to any blood draws scheduled at the same time.
- ^g Includes evaluation of the head, eyes, ears, nose, and throat, and the cardiovascular, dermatological, musculoskeletal, respiratory, gastrointestinal, genitourinary, and neurological systems. Abnormalities observed at baseline should be recorded on the General Medical History and Baseline Conditions eCRF. At subsequent visits, new or worsened clinically significant abnormalities should be recorded on the Adverse Event eCRF.
- ^h All ECGs are to be obtained prior to other procedures scheduled at the same time.
- ⁱ Hematology includes WBC count, RBC count, hemoglobin, hematocrit, platelet count, differential count (neutrophils, eosinophils, basophils, monocytes, lymphocytes, other cells).
- ^j Chemistry panel (serum or plasma) includes sodium, potassium, chloride, bicarbonate, glucose, BUN or urea, creatinine, total protein, albumin, phosphorus, calcium, total and direct bilirubin, alkaline phosphatase, ALT, AST, uric acid, LDH.

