- ^k Only LFTs (AST, ALT, bilirubin, and alkaline phosphatase) will be conducted at these visits. During the Safety Follow-up period, LFTs will be performed every month during the first 6 months and subsequently at each visit occurring approximately every 3 months thereafter, until the end of this period.
- ^l All women of childbearing potential will have a serum pregnancy test at screening. Urine pregnancy tests will be performed at the specified subsequent visits. If a urine pregnancy test is positive, it must be confirmed by a serum pregnancy test. During the Safety Follow-up period, urine pregnancy tests will be performed every month during the first 6 months at each site visit. Urine pregnancy tests will continue to be performed on a monthly basis during the remainder of the Safety Follow-up period with patients performing the test at home (using kits provided by the site) during months where there is no site visit and at each site visit occurring approximately every 3 months. Patients will be instructed to contact the site immediately in case the result of the home pregnancy test is positive. In such cases, the patient must visit the site for a confirmatory serum pregnancy test.
- ^m Open-label treatment with pirfenidone will be started at this visit, if the patient requests continued treatment with pirfenidone.
- ⁿ Handheld spirometry will be conducted by the patient every day in a seated position.
- ^o To provide handling evaluations and quality assurance for the daily spirometer assessments, nursing visits to the patient's home (or at another suitable location) will occur at least three times during the trial, namely between Weeks 1 and 4, between Weeks 8 and 12, and between Weeks 16 and 20. Additional home nursing visits may be conducted according to the investigator's judgment.
- ^p 6-Minute Walk Distance (6MWD) is used to evaluate the functional capacity of patients with lung disease.
- ^q Questionnaires will be self-administered prior to the patient receiving any information on disease status and prior to the performance of non-PRO assessments. Refer to [Appendix 2](#) for copies of the questionnaires and a brief description.
- ^r Includes any medication (e.g., prescription drugs, over-the-counter drugs, vaccines, herbal or homeopathic remedies, nutritional supplements) used by a patient from the washout period until 28 days after the last dose of trial treatment.

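### After Week 24, patients who complete double-blind treatment have no scheduled creatinine during up to 52 weeks of open-label pirfenidone, although renal impairment is a mandatory stop; it could be run on the liver-test sample already drawn

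*Protocol*

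**What the plan says.** Protocol Section 4.6.2 gives four bullets under which trial treatment must stop. One of them is "Hepatic or renal impairment". No renal threshold is attached.

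The rule reaches the open-label year. In the Appendix 1 schedule, the row "Trial treatment administration" is marked at Week 28 and in the additional safety follow-up column. Footnote m reads: "Open-label treatment with pirfenidone will be started at this visit, if the patient requests continued treatment with pirfenidone". On dose, Section 4.3.4 says: "The dose of pirfenidone used during the safety follow-up period is in accordance to section 4.3.2.1". That is the full trial dose.

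Creatinine belongs to the full panel in footnote j: "Chemistry panel (serum or plasma) includes sodium, potassium, chloride, bicarbonate, glucose, BUN or urea, creatinine". The chemistry row places that panel at screening, Day 1, Weeks 4, 12 and 24, and the Early Treatment Discontinuation Visit. Weeks 8, 16 and 20 and all open-label visits carry footnote k: "Only LFTs (AST, ALT, bilirubin, and alkaline phosphatase) will be conducted at these visits". The Week 28 and final safety visits have no chemistry.

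SAP Version 3.0 repeats this schedule in its Appendix 2. Its Section 4.7 names the same four liver tests for the open-label laboratory summaries. Its Section 4.2.5 says that all data recorded in that period will be presented, so an unscheduled creatinine could still be reported.

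**The concern.** Set the 4.6.2 stopping reasons beside the open-label schedule. Pregnancy is tested monthly, partly with home kits. Hepatic impairment and liver-test elevations are covered by liver tests, monthly and then about every three months. Angioedema shows itself clinically. Renal impairment is the one reason that can need a laboratory test to be seen and has none scheduled.

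The protocol treats renal function as relevant to safety: Section 4.1.2 excludes significant renal impairment and creatinine clearance below 30 mL/min. Patients may be up to 85 years old. For a former placebo patient, the open-label year is the first exposure to the drug.

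At stake is whether a creatinine rise without symptoms would be noticed in time for the stopping rule to be applied. Sample size, the primary analysis and the efficacy data are not affected.

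**Working it through.** **Inputs.** Protocol Section 3.2: washout 4 weeks, screening 3, double-blind 24, follow-up 4, open-label up to 52, final visit 4 weeks after the last dose. Protocol Section 4.3.4 and Appendix 1: open-label visits monthly for six months, then about every three months (taken as Months 9 and 12). Section 6.1: about 250 patients, 125 per arm.

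**The plan's own figure.** 4 + 3 + 24 + 4 + 52 + 4 = 91 weeks, which matches the stated maximum.

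**Time without a scheduled creatinine, patients who complete 24 weeks**

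- Last scheduled creatinine: Week 24.
- Open-label dosing: Week 28 to Week 28 + 52 = 80 at most. Final visit: Week 80 + 4 = 84.
- From the last creatinine to the first open-label dose: 28 − 24 = 4 weeks. To the last dose: 80 − 24 = 56 weeks. To the final visit: 84 − 24 = 60 weeks.
- Of those 60 weeks, 4 before and 4 after open-label dosing are off drug: 60 − 8 = 52 weeks on drug.

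**Share of pirfenidone exposure with no scheduled renal test**

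- Former placebo patients: 52/52 = 100%.
- Pirfenidone arm: 52/(24 + 52) = 52/76 = 68%.

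**Scheduled creatinine results for a former placebo patient.** Before open-label drug: screening, Day 1, Weeks 4, 12 and 24 = 5. On drug: 0.

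**With creatinine on the existing liver-test sample.** Open-label visits: 6 + 2 = 8, at about Weeks 32, 37, 41, 45, 50, 54, 67 and 80. The interval from Week 24 to the first is about 8 weeks, then about 4 weeks five times, then about 13 weeks twice. The longest interval between scheduled results is about 13 weeks.

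**Patients concerned.** Open-label uptake is not given. At an assumed 50% to 100% of 125, former placebo patients number 0.5 × 125 = 62.5 (about 63) to 125.

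**Workload.** All rates here are assumptions.

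| | Low | High |
|---|---|---|
| Uptake of 250 patients | 50% | 100% |
| Visits lost to dropout | 25% | 0% |
| Extra creatinine results | 0.5 × 250 × 8 × 0.75 = 750 | 250 × 8 = 2,000 |
| Incidental abnormal share | 1% | 5% |
| Abnormal values to follow up | 750 × 0.01 = 7.5 (about 8) | 2,000 × 0.05 = 100 |

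Missed renal cases cannot be estimated, because the documents give no renal event rate.

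**The case against.** The strongest reply is that the schedule is a risk-based choice. Section 5.1 says: "The anticipated important safety risks for pirfenidone are outlined below". None of the risks in Sections 5.1.1.1 to 5.1.1.8 is renal, and the open-label liver tests follow from the hepatic risk in 5.1.1.1. Weeks 8, 16 and 20 are liver-only too. Patients entering the open-label period have passed the renal exclusions and had five scheduled creatinine results. This stands as a reason for low priority. It does not explain why a mandatory stop that can need a laboratory test has none scheduled during a first exposure.

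A second reply is that a stopping rule does not imply a scheduled test; angioedema has none. That is right, so a reader who inferred that 4.6.2 and footnote k contradict each other would go too far. Nor is renal impairment undetectable on open-label drug. Section 5.3.1 states: "Investigators will seek information on adverse events at each patient contact". Unscheduled tests remain possible, and Section 4.6.1 lets the investigator withdraw a patient for any condition that threatens safety. These safeguards depend on symptoms or suspicion, which a silent creatinine rise need not raise.

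A third reply is that creatinine without an action limit invites inconsistent decisions. The only numeric renal limit is the entry criterion of 30 mL/min by Cockcroft-Gault, which needs weight. Weight is scheduled only at screening, Week 24 and early discontinuation. But the double-blind period already pairs scheduled creatinine with investigator judgment and no threshold, and comparing serum creatinine with the Week 24 value needs no weight.

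Timing is a fair objection. SAP Section 4.5.8 dates the primary analysis to March 2019, and SAP Section 4.2.6 sets its cut-off after the last Week 28 visit. Twelve months of dosing plus 28 days would then end by about April 2020, before SAP Version 3.0 of July 2020.

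**Conclusion.** The point holds as a low-priority improvement to safety monitoring. For patients who complete 24 weeks, up to 52 weeks of open-label pirfenidone run with no scheduled renal test: all exposure for former placebo patients and 68% of the maximum for the pirfenidone arm.

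Three stronger readings are not supported:

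- **Sixty weeks of unmonitored exposure.** That interval includes 8 weeks off drug.
- **Every patient is affected.** Those who stop early have a full panel at the Early Treatment Discontinuation Visit, including those who enter the open-label period from it after unblinding.
- **A renal hazard has been shown.** No renal risk is listed in 5.1.1, and the Investigator's Brochure, which holds the full safety summary, is not among these documents.

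The week counts assume a full 12 months of open-label dosing. The number of patients also depends on uptake, which is not stated.

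**What to change.** 1. Amend Appendix 1 footnote k so that serum creatinine is run on the liver-test sample at the roughly 8 open-label visits. The investigator judges it against the Week 24 value, as creatinine is judged in the double-blind period. The 4.6.2 rule stays as it is.
2. Add creatinine to the open-label laboratory summaries in SAP Section 4.7.

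This does not supply a check at Week 28 before the first open-label dose; that would need a separate draw.

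**Cost.** There is no extra visit or blood draw. Running creatinine on the same sample is an inference, but footnote j lists it with the liver tests in one serum or plasma panel, and Section 4.5.8 sends all laboratory tests to the local laboratory. The cost is one extra analyte per visit and the follow-up of some incidental abnormal values, in the ranges shown above. The change is a protocol amendment. Under Section 9.6 it needs ethics approval and, where locally required, regulatory approval before use, across about 90 sites.

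If open-label dosing has ended, report any unscheduled creatinine under SAP Section 4.2.5 and carry the schedule change into later protocols.
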